### 13.4 Serious Adverse Events

#### 13.4.1 Definition of Serious Adverse Events

A SAE is defined as any untoward medical occurrence that at any dose:

- Results in death
- Is life-threatening
- Requires hospitalization or prolongation of existing hospitalization

- Results in persistent or significant disability or incapacity
- Consists of a congenital anomaly or birth defect
- Is an important medical event as recognized by the investigator

SAEs must be reported to the Sponsor and IRB within 24 hours of site awareness.

#### **13.4.2 Definition of Suspected Unexpected Serious Adverse Reactions**

Suspected unexpected serious adverse reactions (SUSARs) are AEs that are believed to be related to a test product and are both unexpected (i.e., the nature or severity is not expected from the information provided in the IB) and serious. SUSARs are subject to expedited reporting to the IRB (see [Section 15.3.2](#) for details on reporting SUSARs).

#### **13.5 Adverse Events of Special Interest (AESI)**

The following AESI must be reported to the Sponsor within 24 hours of site awareness irrespective of seriousness, severity or causality:

- Serum sickness-like reaction – a type III hypersensitivity reaction presenting with a constellation of symptoms including fever, pruritic rash, joint pain/tenderness/edema/erythema, muscle pain, edema of the lips and/or eyelids, GI symptoms (nausea, vomiting, abdominal cramps, diarrhea), headache and dyspnea
- A new vasculitic rash, a fixed, erythematous, non-blanching rash. Vasculitic rashes may be accompanied by fever, fatigue and diffuse aches or pain
- Urticarial reaction
- Leucocytosis with WBC > 50,000/uL

In the event of a suspected serum sickness-like reaction blood samples will be collected within 1 hour of the event to assess CBC, ESR, urinalysis, serum chemistries, C3, C4 and fibrinogen.

The subsequent course of therapy may include NSAIDs, antihistamines and/or corticosteroids depending on institutional guidelines and the severity of the event.

The investigator is encouraged to discuss with the Sponsor medical monitor all AESI as defined above.

#### **13.6 Safety Laboratory Measurements**

Venous blood and urine samples will be collected from subjects by a trained member of the clinical team.

Safety laboratory tests and virology will be carried out on blood samples, and drugs of abuse tests and urinalysis will be carried out on urine samples. The research will not involve analysis or use of human DNA.

Blood samples will be sent for laboratory testing in linked anonymized form (subject number only). This information can be linked directly to the subject by the Quotient research team and study monitor but not by the laboratory staff or Sponsor.

Blood and urine sample results will be reviewed by a physician and acted upon before the subject is dosed, receives their next dose or is released from the study, as appropriate. A list of the laboratory parameters measured is presented in [Appendix 1](#).

#### **13.6.1 Hematology and Clinical Chemistry**

Laboratory tests will be performed by Quotient Sciences Labs according to the Schedule of Assessments presented in [Appendix 2](#) (Part 1) and [Appendix 3](#) (Part 2). Blood samples will be collected and processed as detailed in the CSPM. Scheduled blood samples will be taken following an overnight fast of a minimum of 8 hours. Samples taken due to early withdrawal do not need to be fasted. The acceptable deviations from the nominal blood sampling times are detailed in the schedules.

CLcr will be calculated at screening by Quotient Sciences Labs using the Cockcroft-Gault equation and body weight for eligibility purposes:

$$\text{CLcr (mL/min)} = \frac{(140 - \text{age [years]}) \times \text{body weight [kg]} (x 0.85, \text{if female})}{72 \times \text{serum creatinine (mg/dL)}}$$

#### **13.6.2 Anti-Drug Antibodies**

Venous blood samples will be withdrawn via venipuncture according to the Schedule of Assessments presented in [Appendix 2](#) (Part 1) and [Appendix 3](#) (Part 2). The acceptable deviations from the nominal blood sampling times are detailed in the schedules.

The timing and number of the samples may be amended by the Sponsor, including collection over a longer duration. Any changes to blood sampling time points would be documented and retained in the TMF.

Samples will be collected into appropriate tubes as specified by the bioanalytical laboratory. Details of sample tubes and processing will be contained in the CSPM.

#### **13.6.3 Urinalysis**

Urinalysis will be performed by Quotient Sciences Labs according to the Schedule of Assessments presented in [Appendix 2](#) (Part 1) and [Appendix 3](#) (Part 2). Urine samples will be collected and processed as detailed in the CSPM. Microscopic analysis of sediment for bacteria, casts, crystals, epithelial cells, red blood cells and white blood cells will be performed, as required. The acceptable deviations from the nominal urine sampling times are detailed in the schedules.

#### **13.6.4 Pregnancy Test**

Serum and urine pregnancy tests will be performed as detailed in [Appendix 2](#) (Part 1) and [Appendix 3](#) (Part 2). The samples will be collected and processed as detailed in the CSPM.

#### **13.6.5 Follicle-Stimulating Hormone Test**

Serum FSH tests will be performed as detailed in [Appendix 2](#) (Part 1) and [Appendix 3](#) (Part 2). The samples will be collected and processed according to the CSPM.

### **13.6.6 Alcohol, Cotinine, and Drug Screen**

A urine alcohol, cotinine and drug screen will be performed by Quotient Sciences Labs according to the Schedule of Assessments presented in [Appendix 2](#) (Part 1) and [Appendix 3](#) (Part 2). The sample will be collected and processed according to the CSPM.

Subjects will be screened for the drugs of abuse listed in [Appendix 1](#). A positive result will exclude the subject from dosing for the remainder of the study.

### **13.6.7 Abnormal Laboratory Findings**

In cases where laboratory findings are outside the normal range and the investigator believes that the results may be of clinical significance, repeat sampling may be requested as clinically indicated. If the abnormal finding is clinically significant, the Sponsor and Medical Monitor may be consulted and appropriate actions will be taken (e.g., the subject will not be entered into or may be withdrawn from the study). The subject will be referred to their primary care provider or other appropriate provider for further care if necessary. The same will apply if the results of the HBsAg, HCV Ab or HIV test are positive and in addition the investigator will ensure that adequate counselling is available if requested.

Abnormal results at follow-up assessments will also require repeat testing if the investigator believes the results may be of clinical significance.

Any clinically significant laboratory finding, including changes from baseline, must be reported as an AE.

Additional blood and/or urine samples may be taken for safety tests. Furthermore, additional assays outside those specified in the protocol may be performed for safety reasons as requested by the investigator.

### **13.7 Vital Signs Measurements**

Blood pressure and heart rate will be measured by an automated recorder after the subject has been in a supine position for a minimum of 5 minutes and body temperature and respiratory rate will be measured according to the Schedule of Assessments presented in [Appendix 2](#) (Part 1) and [Appendix 3](#) (Part 2). The acceptable deviations from the nominal vital signs assessment times are detailed in the schedules.

If a subject shows an abnormal assessment at any stage, repeat measurements may be made and the abnormality followed to resolution if required. Additional measurements may be taken as deemed necessary by the investigator or sub-investigator.

Any clinically significant abnormality, including changes from baseline, must be reported as an AE.

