## 7 Objectives and Endpoints

Objectives	Endpoints
Primary	
To assess the safety, tolerability and PK of single (Part 1) and multiple (Part 2) SC doses of PDM608	
 
Incidence of AEs, change from baseline for physical examinations and vital signs, electrocardiograms (ECGs) and laboratory safety tests including ADA in blood
 
PK parameters for PDM608
 

Secondary	
To assess immunogenicity following single and multiple doses of PDM608	Incidence of ADA in blood
Exploratorya	
To assess PD following administration of single (Part 1) and multiple (Part 2) ascending SC doses of PDM608	
 
Individual baseline corrected leukocyte, Treg and other immune cell numbers/percentages
 
Individual baseline corrected cytokine levels
 

a Exploratory PD biomarker objectives may be reported separately to the Clinical Study Report.

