### 8.2.2 Criteria for Dose Decision

Progression to the next dose group will be permitted after review of defined safety and tolerability data suggests that it is safe to do so. All SAC decisions will be documented and signed by the investigator and Sponsor medical monitor or delegate. Evidence of the decision will be retained in the Trial Master File (TMF).

For dose escalation in the SAD phase to proceed data must be available from a minimum of 6 subjects who have completed the planned safety and tolerability assessments out to 96 hours post-dose (Day 5), to ensure at least 4 subjects receive active IMP. For dose escalation in the MAD phase to proceed data must be available from a minimum of 8 subjects who have completed the planned safety and tolerability assessments out to 96 hours post-final dose (Day 26) to ensure at least 6 subjects receive active IMP.

It is planned that the dose will be escalated for each subsequent cohort; however, the SAC may also agree to enroll additional subjects for an intermediate dose level if warranted or may agree to reduce the dose with no limit on the possible extent of reduction. Any decision to investigate an intermediate or reduced dose level will be fully documented.

The decision to proceed to the next dose level will be based on safety and tolerability and data. The following data are required:

- AEs
- Vital signs
- Safety laboratory, including review of PD hematology parameters outlined in [Section 6.4](#)

- 12-lead ECG
- Physical examinations

The SAC may also consider additional data as it becomes available and as relevant to decisions, including ADA, PD, and PK.

Rules for dose decision are as follows:

- Dose escalation will not be more than 3-fold between SAD cohorts. Anticipated SAD dose levels are described in [Table 2](#).
- Dose escalation will not be more than 3-fold between MAD cohorts.
- Dosing for each MAD cohort will be at a dose level 2-3 fold lower than the highest SAD cohort dose deemed safe by the SAC at the time of each MAD cohort initiation.
- Doses administered will be predicted not to exceed a mean  $C_{max}$  of 103,950 ng/mL and a mean  $AUC_{(0-24h)}$  of 1,775,000 ng.h/mL, which is the sex-averaged mean NOAEL exposure limits after the first dose of 18 mg/kg in the cynomolgus NOAEL 28-day good laboratory practice (GLP) toxicology study, in any individual subject.

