## Appendix 2      Schedule of Assessments: Part 1 Single Ascending Dose

Study Day →	SCRN	D -1	D1				D2	D3	D4	D5	D6	D7	D8	D11	D15	D22	Premature
		Admit	Pre-Dose	0H	1H	3H	12H	24H	48H	72H	96H	120H	144H	168H	240H	336H	504H
Window →	D-28 to -2	Day of	1H j	n/a	±10M	±10M	±1H	±2H	±2H	±2H	±2H	±2H	±2H	±24H	±24H	±24H	
Assessments ↓																	
Informed Consent	X																
Medical History	X	X a															
Weight, Height, BMI	X	X b															
Vein Assessment	X	X															
Urine Alcohol, Cotinine, Drug Screen	X	X															
Serum Pregnancy	X c																
Urine Pregnancy		X d															
Randomization			X e														
IMP Administration f				X													
Physical Exam	X							X		X			X				X
Hem & Chem m	X	X						X	X	X		X		X		X	X
Virology & TB Test	X																
FSH g	X																
CLcr	X							X	X	X		X		X		X	X
Urinalysis	X		X k					X	X	X	X	X	X				
Single ECG	X	X													X	X	X
Triuplicate ECG			X		X	X	X	X	X	X	X	X	X				

Study Day →	SCRN	D -1	D1				D2	D3	D4	D5	D6	D7	D8	D11	D15	D22	Premature
		Admit	Pre-Dose	0H	1H	3H	12H	24H	48H	72H	96H	120H	144H	168H	240H	336H	504H
Window →	D-28 to -2	Day of	1H j	n/a	±10M	±10M	±1H	±2H	±2H	±2H	±2H	±2H	±2H	±24H	±24H	±24H	
Assessments ↓																	
Vital Signs h	X	X	X				X	X	X	X	X	X	X				X
PK			X		X	X	X	X	X	X	X	X	X	X	X	X	X
PD			X				X			X			X	X	X	X	X
ADA			X										X		X	X	X
Adverse Events									X								
Concomitant Medications									X								
Clinical Residency			Clinical Residency admit Day -1, discharge Day 8											RV	RV	RV	

RV = Return Visit

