**Appendix 2 Footnotes**

- a Update of medical history
- b Weight only
- c All female subjects
- d All female subjects, except those confirmed menopausal/post-menopausal by FSH  $\geq 40$  IU/L at screening
- e Subjects will be randomized on Day 1 prior to dosing (1 hour window not applicable)
- f See Pharmacy Manual for details on SC IMP administration
- g Menopausal/post-menopausal female subjects only, to confirm childbearing potential status
- h Vital signs to include blood pressure, heart rate, body temperature, and respiratory rate
- j Within 1 hour prior to IMP administration
- k Urinalysis within 2 hours prior to IMP administration
- m Scheduled blood samples will be taken following an overnight fast of a minimum of 8 hours

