## Appendix 3 Schedule of Assessments: Part 2 Multiple Ascending Dose

Screening through Day 16

Study Day →	SCRN	D -1	D1					D2	D3	D4	D5	D6	D7	D8	D9	D14	D15	D16
Time Relative to D1 →		Admit	Pre-Dose	0H	1H	3H	12 H	24 H	48 H	72 H	96 H	120 H	144 H	168 H	192 H	Admit	336H	360H
Time Relative to Prior Dose →			0H	1H	3H	12 H	24 H	48 H	72 H	96 H	120 H	144 H	168 H	192 H	0H	24H	0H	24H
Window Relative to Prior Dose →	D-28 to -2	Day of	≤1H i	n/a	±10M	±10M	±1 H	±2 H	±2 H	±2 H	±2 H	±2H	±2H	≤1H i	Day of	Day of	≤1H i	Day of
Assessments ↓																		
Informed Consent	X																	
Medical History	X	X a																
Weight, Height, BMI	X	X b																
Vein Assessment	X	X																
Urine Alcohol, Cotinine, Drug Screen	X	X														X		
Serum Pregnancy	X c																	
Urine Pregnancy		X d												X d		X d		
Randomization			X e															
IMP Administrationf				X										X			X	
Physical Exam	X																	
Hem & Chemk	X	X					X			X				X	X		X	
Urinalysis	X	X					X	X		X				X	X		X	
Virology and TB Test	X																	
FSH	X g																	

Study Day →	SCRN	D -1	D1					D2	D3	D4	D5	D6	D7	D8	D9	D14	D15	D16	
			Admit	Pre-Dose	0H	1H	3H	12 H	24 H	48 H	72 H	96 H	120 H	144 H	168 H	192 H	Admit	336H	360H
Time Relative to Prior Dose →																	0H	24H	
Window Relative to Prior Dose →	D-28 to -2	Day of	≤1H i	n/a	±10M	±10M	±1 H	±2 H	±2H	±2H	≤1H i	Day of	Day of	≤1H i	Day of				
Assessments ↓																			
CLcr	X							X							X	X			
Single ECG	X																X		
Triplicate ECG		X	X		X	X	X	X	X	X	X	X	X	X	X		X		
Vital Signs h	X	X	X				X	X	X	X	X	X	X	X	X	X	X	X	
PK			X		X	X	X	X	X	X	X	X	X	X			X		
PD			X					X			X				X			X	
ADA			X												X			X	
Adverse Events	X																		
Concomitant Medications	X																		
Clinical Residency		Admit Day -1, Discharge D9													Admit D14, D/C D16				

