## Day 21 through 60 and Premature Discontinuation

Study Day →	D21	D22				D23	D24	D25	D26	D27	D28	D29	D32	D36	D43	D50	D60	Premature DC
Time Relative to D1 →	Admit	n/a				528H	552H	576H	600H	624H	648H	672H	744H	840H	1008H	1176H	1416H	
Time Relative to Prior Dose →		0H	1H	3H	12H	24H	48H	72H	96H	120H	144H	168H	240H	336H	504H	672H	912H	
Window Relative to Prior Dose →	Day of	≤1H i	±10M	±10M	±1H	±2H	±24H	±24H	±24H	±24H	±24H							
Assessments ↓																		
Urine Alcohol, Cotinine, Drug Screen	X																	
Urine Pregnancy	X d																	
IMP Administration f		X																
Physical Exam																		X
Hem & Chem k	X												X	X	X	X	X	
Urinalysis	X				X	X		X			X	X						
Single ECG														X				X
TriPLICATE ECG	X	X			X	X		X		X		X						X
Vitals Signs h	X	X			X							X	X					
PK		X	X	X	X	X	X	X	X	X	X	X	X	X	X	X	X	
PD		X					X			X		X	X	X	X			X
ADA												X			X		X	X
Adverse Events													X					X
Concomitant Medications													X					X
Clinical Residency		Admit D21, Discharge 29											RV	RV	RV	RV	RV	

RV = Return Visit

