**Appendix 3 Footnotes**

- a Update of medical history
- b Weight only
- c All female subjects
- d All female subjects, except those confirmed menopausal/post-menopausal by FSH  $\geq$  40 IU/L at screening
- e Subjects will be randomized on Day 1 prior to dosing (1 hr window not applicable)
- f See Pharmacy Manual for details on IMP administration
- g Menopausal/post-menopausal female subjects only, to confirm childbearing potential status
- h Vital signs to include blood pressure, heart rate, temperature, and respiratory rate
- i Within 1 hour prior to IMP administration
- k Scheduled blood samples will be taken following an overnight fast of a minimum of 8 hours

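### Appendix 3 schedules no vital signs at 1H or 3H after Part 2 Doses 1 and 4, and Appendix 2 probably has the same gap in Part 1, so early changes lack scheduled, placebo-matched data

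*Combined protocol and SAP*

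**What the plan says.** Section 13.7 leaves timing to the schedules ("body temperature and respiratory rate will be measured according to the Schedule of Assessments presented in" Appendix 2 and Appendix 3) and allows extra measurements at the investigator's discretion. The schedule footnotes define the content: "Vital signs to include blood pressure, heart rate, body temperature, and respiratory rate" in Part 1, and the same four measurements in Part 2.

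Subjects are in the unit during the hours in question. The residency rows read "Clinical Residency admit Day -1, discharge Day 8" for Part 1, and "Admit Day -1, Discharge D9" and "Admit D21, Discharge 29" for Part 2 Doses 1 and 4.

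Vital signs carry weight in the plan. The primary safety endpoint in Section 7 includes "change from baseline for physical examinations and vital signs, electrocardiograms (ECGs) and laboratory safety tests". Section 8.2.2 lists vital signs for the escalation review under the words "The following data are required". Section 14.4 summarises them by treatment, with changes from baseline as required.

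**The concern.** This is a first-in-human study, and Section 6.1 justifies the placebo arm as showing what changes occur without active treatment. That comparison needs readings taken at the same times in both arms, whether or not anyone suspects a problem. If the schedule holds none in the first hours after dosing, the treatment summaries and the committee's review are empty for that period on blood pressure, temperature and respiratory rate.

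Readings taken at discretion do not fill the gap. They are prompted by concern about a particular subject, so they are selective and bring no matching placebo values. The SAC or the Sponsor may change safety time points later (Section 8.2.1), but that cannot recover readings from cohorts already dosed.

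**Working it through.** There is no planned figure to reproduce. The check is to match each row of the schedules to its time columns.

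**Part 2, Dose 1 (Appendix 3, Screening through Day 16).** The study-day header gives Day 1 five columns: pre-dose, 0H, 1H, 3H and 12H. The window row agrees (up to 1 hour before dosing, n/a, ±10M, ±10M, ±1H). Vital signs are marked pre-dose, blank at 0H, 1H and 3H, and marked from 12H. PK and triplicate ECG are marked at both 1H and 3H. The time header repeated above this part of the table is displaced by one column. Taken literally it would put a vital signs mark at 3H, but it would also put PK at admission and none pre-dose, so it cannot be right. The 1H cell is blank on either reading.

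**Part 2, Dose 4 (Appendix 3, Day 21 through 60).** The time row runs 0H, 1H, 3H, 12H, and the window row agrees up to 24H. Vital signs are marked at 0H and 12H and blank at 1H and 3H. PK is marked at both; ECG is marked at neither.

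**Part 1 (Appendix 2).** The study-day header leaves Day 1 only four columns, where pre-dose, 0H, 1H, 3H and 12H need five. The PD, ADA and single-ECG marks fall on sensible days only if Day 2 sits where that header puts it (PD then falls on Days 2, 5 and 8, for example). Two cells are therefore left for 1H, 3H and 12H. Both are blank for vital signs and both are marked for PK. The window row cannot say which two survive: it keeps ±10M, ±10M and ±1H, but has six ±2H cells for the seven times from 24H to 168H, so it lost a different column. Two blanks among three times mean that at least one of 1H and 3H is blank. By analogy with Part 2, both probably are, and the lost column is 12H.

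| Scheduled at 1H and 3H | Part 2 Dose 1 | Part 2 Dose 4 | Part 1 |
|---|---|---|---|
| Vital signs | 0 of 2 | 0 of 2 | at most 1 of 2, probably 0 |
| PK | 2 of 2 | 2 of 2 | at least 1 of 2, probably 2 |
| Triplicate ECG | 2 of 2 | 0 of 2 | at least 1 of 2, probably 2 |

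**First post-dose reading in Part 2.** 12H ±1H, which is 11 to 13 hours after dosing.

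**Subjects (Sections 8.1.1 and 8.1.2).** Part 2: 4 × 9 = 36 active and 4 × 3 = 12 placebo, 48 in all; without optional Cohort 4, 27 + 9 = 36. Part 1: 5 × 6 = 30 active and 5 × 2 = 10 placebo, 40 in all.

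**Readings needed to close the gap.** Part 2: 2 times × 2 doses × 48 = 192 (144 active, 48 placebo), or 4 × 36 = 144 without Cohort 4. Part 1: at most 2 × 40 = 80 (60 active, 20 placebo), or 1 × 40 = 40 if the original table already marks one of the two times.

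**The case against.** The strongest case against is that early safety is already handled and no harm is shown. Subjects are resident and observed by staff (Section 11.2). The Part 1 sentinel pair is reviewed to 72 hours before the rest of the cohort is dosed. Extra measurements are allowed at any time (Sections 13.7 and 13.11), and procedures also follow site SOPs that the documents do not reproduce. No stopping rule in Section 8.5 turns on an early asymptomatic vital sign. The safety analysis is descriptive, with two or three placebo subjects per cohort. Nothing in the documents places an effect at 1 to 3 hours: Section 6.6.3 reports fever, chills and capillary leak in 2 of 21 donors given GM-CSF at 15 mcg/kg/day, without an onset time.

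Much of this stands. Symptomatic events would be seen and recorded. After Dose 1, the triplicate ECGs give heart rate at both times. What the objection does not supply is a scheduled blood pressure, temperature or respiratory rate in both arms at those hours.

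Table damage is a fair second objection. It limits Part 1 to the weaker statement in the working. It also bears on Dose 4: a reader might infer from the same row that no vital signs are taken between 12H and 168H, which would leave the Day 26 review short. The documents do not support building on that. The same table shows no hematology mark from Day 22 to Day 29, although Section 6.4 relies on laboratory values up to 96 hours after the final dose, so this part may be misprinted. The 1H and 3H blanks after Dose 4 are better supported, because the time and window rows agree there and the Dose 1 table shows the same pattern.

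**Conclusion.** The point holds for Part 2 as printed. No vital signs are scheduled at 1H or 3H after Dose 1 or Dose 4, for up to 48 subjects (36 without Cohort 4), while PK is drawn at both times. After Dose 4 there is no ECG at those times either, so heart rate is also unscheduled. For Part 1, at least one of the two times is blank and probably both are, subject to the original table.

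The consequence is limited to missing scheduled, placebo-matched early data on asymptomatic changes. A reader might infer that the primary safety endpoint cannot be assessed, or that early reactions would go unnoticed. Neither follows: change from baseline remains evaluable from later readings, and symptomatic events are covered by observation and discretionary measurements. How many changes would be missed cannot be estimated, because the documents give no onset time.

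The conclusion assumes that the Appendix 3 columns are as the study-day header and window rows show. It is a cheap improvement that should be made, not a defect that undermines the study.

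**What to change.** In Appendix 3, mark vital signs at 1H and 3H after Doses 1 and 4. In Appendix 2, check the original table and mark 1H and 3H wherever they are blank. Take the readings alongside the existing PK draws, within the same ±10-minute windows; PK keeps the nominal time and any ECG comes before vital signs, as Section 10.3.2 already orders. Include both times in the change-from-baseline summaries by treatment under Section 14.4.

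The cost is 192 readings in Part 2 (144 without Cohort 4) and up to 80 in Part 1, at most 272 for the planned subjects. If every permitted replacement is dosed (60 and 50 subjects, Section 8.4), the ceiling is 4 × 60 + 2 × 50 = 340. All fall during residency at times staff already attend for PK, so no visit or blood draw is added. The drawback is a slightly busier post-dose period.
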